Patient answers Patient Satisfaction Questionnaire in UAB Orthodontic Clinic.	10-15 minutes	twice, at each follow-up visit	 Res  Routine
Patients will be evaluated for reduction of white spot lesions.	~10 minutes	once, at end of treatment	 Res  Routine

- f. Will an interview script or questionnaire be used? Yes No
If Yes, attach a copy.

- g. Will participants incur any costs as a result of their participation? Yes No
If Yes, describe the reason for and amount of each foreseeable cost.

- h. Will participants be compensated? Yes No
If Yes, complete i-v:
 i. Type: (e.g., cash, check, gift card, merchandise): Visa gift card
 ii. Amount or Value: \$25.00
 iii. Method (e.g., mail, at visit): one-time issuance per patient, at clinic visit
 iv. Timing of Payments: (e.g., every visit, each month): upon completion of clinical trial
 v. Maximum Amount of Payments per Participant: \$25.00

17. Describe the potential benefits of the research.

You may or may not benefit directly from taking part in this study. Although white spot lesions may appear less noticeable and teeth may feel less sensitive to hot or cold temperatures, this is not guaranteed. You will not benefit financially from any commercial gains from sales of any product resulting from this study. Research carried out on your results may lead to the development of marketable procedures, and any benefit from the commercial products will remain with the sponsor.

18. Risks

- a. List the known risks—physical, psychological, social, economic, and/or legal—that participants may encounter as a result of procedures required in this protocol. Do not list risks resulting from standard-of-care procedures. *Note: Risks included in this protocol document should be included in the written consent document.*
- Skin allergic reaction (such as hives, swelling of the face, lips, tongue and/or throat which may cause difficulty in breathing or swallowing, and if not treated promptly could become life-threatening) due to contact with the device or its components. The types of materials that may come into contact with the skin include polyurethane, polycarbonate, neoprene, nylon, and styrene-butadiene. No latex is included in the OrthoPulse™.

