 - If you are, or will be, using any medication, herbal or “natural” remedy, during the course of this study, please inform your study orthodontist immediately. Please check with the study orthodontist before you begin taking a new medication while in this study.
 - Low level laser light exposure to the eye (if the Face Frame is not properly worn during the treatment). Do not stare directly at the light, and close your eyes when taking the headset on and off.
 - By signing the Informed Consent, parent or guardian agrees to be present at (and monitor) all device applications of their child.
- b. Estimate the frequency, severity, and reversibility of each risk listed.
upon contact, mild, discontinue contact
- c. Is this a therapeutic study or intervention? Yes No
If Yes, complete the following items:
- i. Describe the standard of care in the setting where the research will be conducted: _____
 - ii. Describe any other alternative treatments or interventions: You may choose not participate in the Clinpro™/MI-Paste Plus™ study and still receive routine orthodontic treatment in the UAB Orthodontic Clinic.
 - iii. Describe any withholding of, delay in, or washout period for standard of care or alternative treatment that participants may be currently using: none
- d. Do you foresee that participants might need additional medical or psychological resources as a result of the research procedures/interventions? Yes No
If Yes, describe the provisions that have been made to make these resources available.

- e. Do the benefits or knowledge to be gained outweigh the risks to participants? Yes No
If No, provide justification for performing the research: _____

19. Precautions/Minimization of Risks (If study involves drugs or devices complete the Drug or Device Review Sheet and skip to question #20)

- a. Describe precautions that will be taken to avoid risks and the means for monitoring to detect risks.
- Patient education and examination at regularly-scheduled follow-up visits
 - By signing the Informed Consent, parent or guardian agrees to be present at (and monitor) all device applications of their child.
- b. If hazards to an individual participant occur, describe (i) the criteria that will be used to decide whether that participant should be removed from the study; (ii) the procedure for removing such participants when necessary to protect their rights and welfare; and (iii)

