any special procedures, precautions, or follow-up that will be used to ensure the safety of other currently enrolled participants.

All patients have the ability to stop using the product if adverse effects occur. This will be reported to PI who will stop the trial if necessary.

- c. If hazards occur that might make the risks of participation outweigh the benefits for all participants, describe (i) the criteria that will be used to stop or end the entire study and (ii) any special procedures, precautions, or follow-up that will be used to ensure the safety of currently enrolled participants.
- Excessive whitening of teeth
 - Inflammation of tissues

20. Informed Consent

- a. Do you plan to obtain informed consent for this protocol? Yes No

If Yes, complete the items below.

If No, complete and include the [Waiver of Informed Consent](#) or [Waiver of Authorization and Informed Consent](#), as applicable.

- b. Do you plan to document informed consent for this protocol? Yes No

If Yes, complete the items below.

If No, complete the items below **and** include the [Waiver of Informed Consent Documentation](#).

- c. How will consent be obtained? by interview

- d. Who will conduct the consent interview? PI or Research Coordinator

- e. Who are the persons who will provide consent or permission? patients or their parents

- f. What steps will be taken to minimize the possibility of coercion or undue influence?
Patients will neither be encouraged nor discouraged to participate in the trial.

- g. What language will the prospective participant or the legally authorized representative understand? English only

- h. What language will be used to obtain consent? English only

- i. If any potential participants will be, or will have been, in a stressful, painful, or drugged condition before or during the consent process, describe the precautions proposed to overcome the effect of the condition on the consent process. If not, enter "no such effect."
no such effect

- j. If any project-specific instruments will be used in the consenting process, such as flip charts or videos, describe the instrument(s) here, and provide a copy of each. If not, enter "not used."
not used

- k. How long will participants have between the time they are told about the study and the time they must decide whether to enroll? If not 24 hours or more, describe the proposed time interval and why the 24-hour minimum is neither feasible nor practical. 30 minutes

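### Item 18a lists risks of a light-emitting device that is not in this trial and no risk of the three study pastes, although the form directs its risks into the consent document

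*Protocol*

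**What the plan says.** Protocol items 13, 15d, 16a and 16e describe one kind of intervention: Clinpro 5000, Clinpro Tooth Crème or MI-Paste Plus, brushed on at home twice a day for 4 months, with 30 participants per product and 90 in all.

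Item 18a asks for the known risks of the procedures this protocol requires and leaves out standard-of-care risks. Its note adds: "Risks included in this protocol document should be included in the written consent document". The answer has four bullets:

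1. An allergic skin reaction, attributed to a device and its materials, ending with "No latex is included in the OrthoPulse™".
2. A request to tell the study orthodontist about medication.
3. "Low level laser light exposure to the eye (if the Face Frame is not properly worn during the treatment", followed by advice on putting a headset on and taking it off.
4. A statement that, by signing consent, a "parent or guardian agrees to be present at (and monitor) all device applications of their child".

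Item 18b covers all of these in one line and grades severity as mild. Item 19a gives two precautions: "Patient education and examination at regularly-scheduled follow-up visits", and the parental sentence again. Item 19b says "All patients have the ability to stop using the product if adverse effects occur". Item 19c, on hazards that could end the whole study, lists "Excessive whitening of teeth" and "Inflammation of tissues".

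**The concern.** The risk section appears to describe a different product. Its allergens are appliance materials such as polycarbonate and neoprene, its eye hazard is laser light, and its safeguard for children is supervision of a device. A participant in this trial meets none of these. Nothing in 18a says what might happen to someone who brushes with one of the three pastes for 4 months.

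This matters because the form treats 18a as source text for consent. Several bullets already address the reader as a consent form would. Copied across as the note directs, they would give adolescents and parents a wrong account of the risks and ask parents to supervise applications that never take place. Item 20k allows 30 minutes to decide, which leaves little time to notice or query the mismatch. The IRB's own weighing of risk and benefit in 18e would also rest on another product's risks.

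**Working it through.** The plan gives no figure to reproduce. The check sets 18a against the rest of the documents and counts.

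**Is there a light-emitting device in the trial?**

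| Place | Intervention described | Light device? |
|---|---|---|
| Item 13, purpose | three pastes | no |
| Item 15d, groups | three groups of 30, one paste each | no |
| Item 16a, methods | home brushing after a non-fluoride washout | no |
| Item 16e, procedures table | caries risk assessment, brushing, reviews, questionnaire, lesion evaluation | no |
| SAP | comparison on enamel decalcification scores | no |

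The tick marks for items 7 and 8 (drugs, devices) did not survive in the text. No surviving narrative describes a study device, and OrthoPulse is named only in 18a.

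**What do the 18a bullets cover?**

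| Bullet | Subject | Device | General | Paste |
|---|---|---|---|---|
| 1 | contact allergy to device materials | 1 | 0 | 0 |
| 2 | reporting medication | 0 | 1 | 0 |
| 3 | laser light to the eye | 1 | 0 | 0 |
| 4 | parental presence at device applications | 1 | 0 | 0 |
| Total | 4 | 3 | 1 | 0 |

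Only bullets 1 and 3 state a risk; bullet 4 is a condition of consent. So 3 of 4 bullets concern the device, 2 of 4 state a device risk, and 0 of 4 name a paste risk. In 19a, 1 of 2 bullets carries the device wording.

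**Does the protocol mention possible paste hazards elsewhere?** It names three that could apply: casein allergy (15c, exclusion 5), excessive whitening and tissue inflammation (both 19c). That is 1 + 2 = 3, of which 0 appear in 18a. The documents do not attribute any of the three to a particular paste, so the link is an inference.

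**Could 18a be read another way?**

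- If the device were part of routine care, 18a's own instruction would exclude its risks.
- If the word device meant the pastes, a face frame, a headset and laser light would make no sense.
- If bullet 1 were meant to cover allergy to a paste, it would not attribute the reaction to the device and list its plastics and rubbers.
- The bullets are intact sentences and one recurs in 19a, so this is not redaction or extraction loss.

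**Related inconsistencies.** Item 16a expects no danger or discomfort beyond the brushing instructions, while 19c names two hazards serious enough to bear on stopping the study. Item 18b grades severity as mild, while 18a says the allergic reaction may threaten life if not treated promptly.

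**The case against.** The strongest reply accepts the text and disputes its weight. The harm is conditional: the consent pages are not available, their absence is no evidence of error, and the correct risks may have been given there or on a Drug or Device Review Sheet. Safety monitoring does not depend on 18a alone, because the follow-up examination in 19a and the stopping text in 19b apply to any product. No analysis is touched.

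The supporting points can also be pressed:

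- The documents never say that a study paste contains casein, and the exclusion itself keeps known reactors out.
- Item 19c does not attribute its hazards to the pastes and might also have come from another study.
- Item 16a speaks of what is expected, and 19c of a contingency.
- The conflict between 18a and 18b disappears once the device text is removed.

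Much of this stands as a limit. What participants were told is unknown, monitoring is only partly affected, the count of three hazards rests on what could apply, and the 18b point is secondary. None of it explains why a paste trial's risk item describes a light device and is silent on the pastes.

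**Conclusion.** The concern holds. Item 18a gives the wrong product's risks in 3 of its 4 bullets (counting the consent condition) and names no paste risk in any of them; 19a repeats the device wording in 1 of 2. This conclusion needs only the protocol and SAP text.

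Two further statements carry assumptions. The effect on participants assumes that 18a was carried into the consent document as the form directs. The finding that 0 of 3 hazards named elsewhere are in 18a assumes that those hazards relate to the pastes. Whether or not either assumption is met, 18a is wrong as written. It should be corrected before anyone relies on it, because it is the protocol's statement of risk to participants who include minors. Endpoints, analysis and sample size are unaffected.

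**What to change.** - Delete the OrthoPulse, laser, face-frame and headset text from 18a.
- List there the known risks of each of the three pastes, taken from their product information. The documents do not contain that information, so the investigator must supply it.
- Reconcile the new list with exclusion 5 in 15c, the two hazards in 19c and the statement in 16a. Rewrite 18b so that frequency, severity and reversibility are given for the risks actually listed.
- Reconcile the parental-presence sentence in 18a and 19a with the products used at home.
- Check the consent document, and any Drug or Device Review Sheet, against the corrected list.

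The cost is an IRB wording amendment to 18a, 18b and 19a, and a check of the consent document. The design and the 90-participant sample size do not change.

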# **Comparison of Clinpro™ 5000 1.1% Sodium Fluoride Anti-Cavity Toothpaste, Clinpro™ Tooth Crème, and MI-Paste Plus for the Prevention and Reduction of White Spot Lesions in Orthodontic Treatment**

## **RESULTS AND STATISTICS**

The results will be evaluated in the following manner:

- (1) Difference in prevention of white spot formation between the control and the study groups using the EDI scores
- (2) Standard statistical methods were employed to analyze all data.

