The purpose of the study is to determine if Clinpro™ 5000, Clinpro™ Tooth Crème, or MI-Paste Plus has an effect on the formation and resolution of white spot lesions for patients undergoing orthodontic treatment. This study will include 90 patients in the UAB Orthodontic Clinic.

14. Background—in nontechnical, lay language

Summarize in 2-3 paragraphs past experimental and/or clinical findings leading to the formulation of this study. Include any relevant past or current research by the Principal Investigator. For drug and device studies summarize the previous results (i.e., Phase I/II or III studies).

During the course of orthodontic treatment, the practitioner normally faces two common iatrogenic treatment side effects: root resorption and enamel decalcification, with the latter occurring at a much higher frequency. While the processes that lead to enamel demineralization are understood, methods to diminish or perhaps eliminate degradation of enamel surfaces are being searched for. Several approaches have been formulated to counteract demineralization of tooth structure. One approach involves patient compliance and consists of in-depth oral hygiene instructions, in-office fluoride applications, and at-home fluoride rinses, gels, and varnishes. An alternative approach, which possesses potential benefit regardless of patient compliance, includes the use of fluoride-releasing agents, such as composites, glass ionomers, sealants, and elastomeric ties.

Enamel decalcification or white spot formation, is a phenomenon occurring primarily on smooth enamel surfaces of teeth, notably within the gingival third of the crown. Demineralized enamel, the precursor to caries formation, can be attributed to fixed orthodontic appliances, and prolonged exposure to bacterial plaque. Bacterial plaque promotes the accumulation of acidic byproducts and demineralization that leads to successive changes in the optical properties of subsurface demineralized enamel. Progression to clinically detectable white spot lesions may occur as early as one month following the placement of orthodontic appliances.

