Over the past thirty years, numerous studies have reported an increase in white spot lesions following orthodontic treatment. While a large portion of the non-orthodontically-treated population experiences some form of decalcification, orthodontically treated patient populations have shown both an increase in new lesions and an increase in the severity of preexisting enamel opacities. Approximately, 50 percent of orthodontically treated patients develop white spot lesions in one or more teeth, compared with only 24 percent in those not undergoing orthodontic treatment.

Appliance removal halts white spot formation, and further elimination of cariogenic factors through diligent oral hygiene efforts inactivates incipient lesions, which may undergo regression over time. Complete elimination of lesions is unlikely due to the rapid remineralization of the enamel surface with high concentration fluorides, which restrict passage of ions into the deeper, more affected layers. Therefore, immediate application of high concentration of fluoride is not recommended. Decreased enamel discolorations may occur with time due to further remineralization, but regression is primarily credited to gradual surface abrasion of tooth structure.

Such problems with enamel decalcification in orthodontic patients have influenced clinicians to search for a solution to orthodontic-associated demineralization. Because fluoride treatment immediately upon debonding is not advocated, clinicians have proposed fluoride treatment and fluoride-releasing materials at the commencement of therapy. Recommended solutions include oral hygiene instruction and reinforcement, fluoridated toothpastes, varnishes and mouthwashes, and fluoridated water supply. Lack of patient compliance hinders these efforts.

Two new anti-cavity toothpastes, Clinpro™ 5000 with 1.1% Sodium Fluoride and Clinpro™ Tooth Crème with 0.21% Sodium Fluoride, are currently available and have been shown in some initial case reports to be useful in the reduction of white spot lesions. Clinpro™ restores minerals and helps you produce saliva. Both the Clinpro™ products are advanced formulas containing an innovative tri-calcium phosphate ingredient. They are available exclusively from 3M ESPE. Clinpro™ contains fluoride as well as calcium and phosphate, which are components naturally found in saliva.

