2. Patients that in the opinion of the investigator will be compliant with the use of the paste
3. Patients who have not used extensive fluoride regimes
4. 12 years and older
5. Subjects must use a non-fluoridated toothpaste (such as Tom's of Maine) for a one-week period prior to starting this trial.

EXCLUSION CRITERIA

1. Any medical or dental condition that in the opinion of the investigator could impact study results during the expected length of the study.
2. Patient is currently using any investigational drug.
3. Patient plans to relocate or move within six months of enrollment.
4. Patients who have or are currently undergoing fluoride treatment for white spot lesions.
5. Patients with IgE Casein Allergy

d. If participants will comprise more than one group or stratification, describe each group (e.g., treatment/intervention, placebo, controls, sham treatment) **and** provide the number of participants anticipated in each group.

Three groups of 30 subjects (one group with Clinpro™ 5000, one group with MI-Paste Plus, and one group with Clinpro™ Tooth Crème) each will be evaluated as a protocol for the reduction of white spot lesions at the start of orthodontic treatment. Subjects will be recruited through the Orthodontic Postgraduate Clinic at the University of Alabama at Birmingham School of Dentistry.

In order to fully evaluate each of the products, the selected product will be brushed on for two minutes twice daily for 4 months. After brushing on the product, patients should not rinse their mouths with water. Rather, they should just expectorate (spit) so they don't clear out the actives from the product. Patient should also not eat or drink for 30 minutes following the treatment.

Subjects will be reviewed every 4 weeks. Subjects and study administrator will not know if the investigational paste or placebo is being administered. However, the PIs will know. [name] and [name] will randomly choose subjects by drawing individual slips of paper from an envelope on which 30 of each study product (i.e., Clinpro™ 5000, MI-Paste Plus, or Clinpro™ Tooth Crème) will be written. Each subject will receive product based upon the treatment type written on the paper selected by PIs.

- e. Indicate which, if any, of the special populations listed below will be involved in the protocol. Include the Special Populations Review Form (SPRF) if indicated.
- Pregnant Women: Attach [SPRF—Pregnant Women, Fetuses, Neonates/Nonviable Neonates](#)

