- We will require all patients a two weeks washout period, during which time we will give them very specific brushing instructions for using a non-fluoridated product such as Tom's of Maine toothpaste. These are the same instructions that we will require them to follow with whichever product that the patient will later be randomized to use in the trial, i.e. Clinpro™ 5000, Clinpro™ Tooth Crème, or MI-Paste Plus. This will ensure that all patients will use the same application technique, even though not all patients would be of the same level of potential decay. This washout period will last the same length of time for all patients, even though it will not begin simultaneously for all patients.
- Patient will brush on randomized product for two minutes twice daily for 4 months. After brushing on the product, patients should not rinse their mouths with water. Rather, they should just expectorate (spit). Patient should also not eat or drink for 30 minutes following the treatment. No other inconvenience, danger, or discomfort is expected as a result of study methodology.
- b. What is the probable length of time required for the entire study (i.e., recruitment through data analysis to study closure)?

16 weeks

- c.** What is the total amount of time each participant will be involved?
Subjects will be reviewed every 4 weeks. Subjects will be reviewed on four weekly intervals.
- d.** If different phases are involved, what is the duration of each phase in which the participants will be involved? If no phases are involved, enter "not applicable."
not applicable

- e. List the procedures, the length of time each will take, and the frequency of repetition, and indicate whether each is done solely for research or would already be performed for treatment or diagnostic purposes (routine care) for the population. *Insert additional table rows as needed.*

Procedure	Length of Time Required of Participants	Frequency of Repetition	Research (Res) -OR- Routine Care
A caries risk assessment will be used to determine the caries risk of all patients enrolled into the study.	~10 minutes	once, at start of treatment	 Res  Routine
Patient brushes on study paste at home.	2 minutes	twice daily	 Res  Routine
Patients will be reviewed every 4 weeks		twice, every 4 weeks	 Res  Routine

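### The SAP's only listed contrast is against a control group, but none of the three randomised products is designated as the control

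*SAP*

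**What the plan says.** - **SAP, RESULTS AND STATISTICS, item (1):** the only contrast given is "Difference in prevention of white spot formation between the control and the study groups using the EDI scores". It has one control and more than one study group.
- **SAP, same section, item (2):** "Standard statistical methods were employed to analyze all data". This names no test, contrast or reference, and it is in the past tense.
- **Protocol 15d, arms:** "Three groups of 30 subjects (one group with Clinpro™ 5000, one group with MI-Paste Plus, and one group with Clinpro™ Tooth Crème". The randomisation slips come from "an envelope on which 30 of each study product (i.e., Clinpro™ 5000, MI-Paste Plus, or Clinpro™ Tooth Crème) will be written", so all three products carry the same label.
- **Protocol 15d, blinding:** "Subjects and study administrator will not know if the investigational paste or placebo is being administered".
- **Protocol 13 (Purpose):** the aim is to "determine if Clinpro™ 5000, Clinpro™ Tooth Crème, or MI-Paste Plus has an effect on the formation and resolution of white spot lesions". The three products are treated alike.
- **Protocol 14 (Background):** "Two new anti-cavity toothpastes, Clinpro™ 5000 with 1.1% Sodium Fluoride and Clinpro™ Tooth Crème with 0.21% Sodium Fluoride, are currently available". This is the only text that sets two of the products apart from the third.
- **Protocol 16a:** "We will require all patients a two weeks washout period", on a non-fluoridated toothpaste, before the randomised product is started.

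**The concern.** A contrast between a control and study groups needs to know who the controls are. If no arm holds that role, the analyst must assign it, and nothing in the text fixes the assignment before EDI scores are looked at. Making MI-Paste Plus the reference asks whether either Clinpro product differs from it. Making Clinpro 5000 the reference asks whether either of the other two differs from the high-fluoride paste. These are different questions and can give different headline results from the same data.

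There is also a risk of misreading. The words control and placebo suggest that the trial can show an effect against something inactive. It has only three active products, so similar EDI scores in all arms would fit both the case where all work and the case where none does. Section 13's question of whether a product has an effect cannot be answered against placebo, no treatment or ordinary toothpaste, whichever product becomes the reference.

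**Working it through.** **1. Is there room for a control arm?** Protocol 13 and 15a give a total of 90, and 15d gives three arms of 30. 3 × 30 = 90, which reproduces the stated total. No patients are left for a fourth arm, so any control must be one of the three products.

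**2. Does any text give one of them that role?**

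| Candidate | Where | Why it does not settle the matter |
|---|---|---|
| Placebo | Protocol 15d, blinding | Matches no arm and names no product |
| Controls | Protocol 15d, question text | Part of the IRB form's own prompt |
| Non-fluoridated toothpaste | Protocol 15c and 16a | Used by every patient before the randomised product |
| MI-Paste Plus, as the one product not called new | Protocol 14 | Background description; sections 13 and 15d treat the three alike |

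The designated control group is therefore 0 of 90 patients.

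**3. How many readings fit?** There are 3 choices of control. Each can be read as two 30 v 30 contrasts or as one pooled 30 v 60 contrast, giving 3 × 2 = 6 readings. The form matters too. With a normal approximation, two-sided 5% and 80% power (both assumed), the detectable difference is (1.960 + 0.842) × √(1/n₁ + 1/n₂):
- 30 v 60: 2.802 × √(1/30 + 1/60) = 0.63 SD
- 30 v 30, unadjusted: 2.802 × √(2/30) = 0.72 SD (0.74 SD with the t distribution)

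**4. What could an open choice do to the error rate?** The documents state no significance level. Assumptions: two-sided 5%, normal outcome, equal variances, 30 per arm, no dropout, no true differences. Residual degrees of freedom are 90 − 3 = 87. The Dunnett critical value c solves P(|t₁| ≤ c and |t₂| ≤ c) = 0.95 with correlation 0.5, which gives c = 2.25. Rates by simulation (at least 200,000 trials per setting):

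| Reference | Dunnett-adjusted | Unadjusted |
|---|---|---|
| Fixed in advance, two contrasts | 5.0% | about 9% |
| Chosen after seeing the data | about 6.9% | about 12% |

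Read down each column, the open reference adds about 2 points with adjustment and about 3 without. The rest of the gap from 5% to 12% comes from not adjusting. Choosing afterwards among the three pooled 30 v 60 contrasts also gives about 12%.

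**5. What would the repairs cost in power?** Take a true difference of 0.74 SD between two arms. The noncentrality is 0.74 × √(30/2) = 2.87.
- Single unadjusted t-test (58 df): 80%
- Global three-arm F-test, then pairwise tests at 5%: about 77% if the third product equals one of the two, about 70% if it lies midway. The family-wise error with no differences is 5.0%.
- Dunnett against a named reference: 73% for each contrast, wherever the third product lies
- Difference detectable with 80% power: 0.74 SD unadjusted, 0.80 SD with Dunnett

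EDI area scores run from 0 to 3 (SAP, Figure 1) and are ordinal, so these power figures are approximate.

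**The case against.** The strongest reply is that the intention is plain enough. The title announces a comparison of three named products, and that comparison can be run. The word control may be left over from another document, as the placebo wording may be and as the device and laser risks in Protocol 18a evidently are. Alternatively, one control and several study groups fits MI-Paste Plus against the two new Clinpro products. Both readings are reasonable, but they lead to different analyses, and the text commits to neither. That two sensible readers could differ is the defect.

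Four narrower points stand and limit the claim:
- The 12% figure should not be set against 5.0% alone, because most of that gap is missing multiplicity adjustment. The like-for-like figures are 5.0% to about 6.9%, and about 9% to 12%.
- Naming the contrast is necessary but not sufficient. The SAP also gives no patient-level EDI summary, time point or test.
- The lack of an inactive arm is a design limit that would remain even if a reference were named. It bears on what may be claimed, not on whether item (1) is defined.
- The SAP mixes tenses, so the analysis may already be done. Advance specification would then be impossible.

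The statement that no control is designated covers the public text. The opening pages of the protocol form and the attached clinical trial agreement were not available.

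**Conclusion.** The concern holds. The only contrast in the SAP refers to a control group that the design does not contain or designate. Item (1) conflicts with the arm list and cannot be carried out as written; this is more than missing detail. The conclusion rests on reading the two documents together and on 3 × 30 = 90, and it needs no statistical assumption. The error rates and power figures are illustrations under an assumed two-sided 5% level and a normal outcome. They do not suggest that anyone chose the reference after seeing data. Because this is the plan's sole stated comparison, it must be corrected before any result can be presented as pre-specified.

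**What to change.** First establish whether EDI scores have been examined. If they have, date the change and report the resulting analysis as post hoc; neither option below then restores pre-specification. If they have not, replace the control-versus-study-groups wording in SAP item (1) with one of these:

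- **Option A:** *among the three randomised products*. Use a global three-arm test at two-sided 5%, then the three pairwise contrasts at 5% each only if the global test is significant. With three arms this holds the family-wise error at 5%. It is the option closest to the title.
- **Option B:** *between [one product, named by the sponsor as reference] and each of the other two products*. Use two contrasts with Dunnett adjustment at family-wise two-sided 5%. This drops the pooled 30 v 60 reading and leaves the two non-reference products uncompared with each other.

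With either option, reconcile the placebo wording in Protocol 15d with the three-arm list. State in Protocol 13 and in the SAP that conclusions are relative among the three products, with no claim against placebo, no treatment or ordinary toothpaste.

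The cost is wording, a narrower claim and the loss of power shown above; no patients are added. The primary EDI summary, its time point and any baseline adjustment also need defining, but that is a separate point.
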